4. To compare proportion of patients needing extra prednisone to control flares.
5. To compare the proportion of patients with intra-articular injections.
6. To compare the proportion of patients who have at least one flare confirmed by the investigator during the protocol.
7. To compare the area under the curve of the means of the FLARE at one year with a self-assessment questionnaire.
8. To compare the proportion of patients in DAS28 remission and in DAS28 low disease activity at 7 and 12 months between the groups.
9. To compare the medians of HAQ at 4, 7 months and 1 year between the groups.
10. To compare the medians of RAID at 4, 7 months and 1 year between the groups.
11. To compare the medians of the EQ-5D at 4, 7 months and 1 year between groups.
12. To compare the medians of the FACIT-F at 4, 7 months and 1 year between groups.
13. To compare the proportion of patients with “serious” adverse events at 1 year between the groups.

STAR – Statistical Analysis Plan
V3, June 2023

Page 9 of 96

5) Study Population

a. Inclusion Criteria

- Patients aged ≥ 18 years.
- Fulfilling the 2010 ACR/EULAR criteria for RA.
- Treated with a stable dose of sDMARDs or bDMARDs for at least 3 months.
- Who have been treated with prednisone or prednisolone for at least 6 months.
- With a stable dose of prednisone or prednisolone of 5mg/day for at least 3 months.
- With a DAS28 ≤ 3.2 for at least 3 months.
- Patients with health insurance.
- Patients who have signed a written informed consent form.

b. Non-inclusion Criteria

- Any chronic condition that would need long term corticoid use (e.g. chronic lung diseases).
- Evidence of a flare within the last 3 months.
- Evidence of an allergy or intolerance to hydrocortisone or prednisone.
- Chronic idiopathic, or autoimmune clinical adrenal insufficiency.
- GC joint injections within the last 3 months or scheduled in the next 3 months.
- Any GC intake expected more than $>5\text{mg/day}$ within the next 12 months (i.e. administration with rituximab, multiple sclerosis requiring frequent GC infusions,...).
- Any disease with GC contraindication.
- Association with sultopride and with live vaccines.
- Significant trauma or major surgery within the 3 months prior to the baseline visit.
- Scheduled surgery in the next 12 months.
- Fibromyalgia.
- Foreseeable poor compliance with the strategy.

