- Hypotension.
- Biological abnormality such as hyponatremia, hyperkalemia, renal salt loss and hypoglycemia.

If an acute adrenal insufficiency is suspected, an extra visit will be performed in emergency and if the acute adrenal insufficiency is confirmed, the patient will be hospitalized to be treated at the choice of the investigator. If the serum cortisol dosage confirms clinical adrenal insufficiency, an open hydrocortisone therapy by hydrocortisone 20mg/d will be started and an appointment with the endocrinologist will be made. If the serum dosage does not confirm adrenal insufficiency, hydrocortisone will be stopped and other causes of the symptoms will be investigated. If no severe concomitant disease is found, the patient will be able to go back to her/his step of the protocol.

All clinical adrenal insufficiency reports will be reviewed by an independent committee to decide whether, according to the report, the diagnosis of clinical adrenal insufficiency can be validated and recorded for the study. This will be declared as a serious adverse event.

It is expected that less than 1% of patients in this study will experience clinical adrenal insufficiency.

3. Proportion of patients with biological adrenal insufficiency.

Two blood tests will be scheduled with a Synacthène® test at 4 and 7 months. A pathological Synacthène® test will be diagnosed if one hour after Synacthène®, serum cortisol is below 200 ng/mL or 600 nmol/L, or 20 µg/100 ml. In case of abnormal test at the latest Synacthène® test another Synacthène® test will be realized at M12.

4. Proportion of patients who needed a short rescue GC treatment during the protocol.
5. Proportion of patients who needed a GC intra-articular or peri-articular injection during the protocol related to the RA.
6. Proportion of patients with a flare confirmed by the clinician. In case of symptoms of flare, the patient will have an extra visit at her/his center. For DAS28 >3.2, a flare will be confirmed. A flare will be also diagnosed if the DAS28 is >3.2 at any scheduled visits.
7. The area under the curves of the self-administered Flare Assessment in Rheumatoid Arthritis (FLARE) questionnaire. FLARE is an approved self-assessment questionnaire that will be completed at each visit and in case of FLARE at home by the patient. The results are expressed as continuous data. The area under the curve of all the questionnaires will be the variable analyzed.

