
Presence of biological adrenal insufficiency at one year (yes/no)
	
From the variables “ Test performed (Synacthen test) (yes/no) ” at M12 [CRFp127], “ Is the Synacthen test considered pathological? (yes /no) ” to M12 [Derived variable], “ Has hydrocortisone treatment been received in addition to the protocol since the last consultation? » and “ Biological signs of chronic adrenal insufficiency ” [CRFp111], we define 2 modalities:
 
" If yes :
 
 • “ Test carried out (Synacthen test) ” = Yes • AND “ Is the Synacthen test considered pathological? » = Yes 
OR
 
 • “ Has hydrocortisone treatment been received in addition to the protocol since the last consultation? » = Yes • AND “ Biological signs of chronic adrenal insufficiency ” = Yes 
" Not if :
 
 • “ Test carried out (Synacthen test) ” = No • AND “ Has hydrocortisone treatment been received in addition to the protocol since the last consultation? » = No 
OR
 
 • OR if “ Test carried out (Synacthen test) ” = Yes • AND “ Is the Synacthen test considered pathological? » = No • AND “ Has hydrocortisone treatment been received in addition to the protocol since the last consultation? » = No

STAR – Statistical Analysis Plan
V3, June 2023

Page 68 of 96

4) Proportion of Patients Needing Supplemental Prednisone to Control Flares

Proportion of patients who required salvage GC treatment during the protocol.

To meet this secondary endpoint, we will use the Treatment Compliance Variables at M4, M7, M9, M12, Vadd 1 and Vadd2 which will be combined to create a new binary derived variable as presented below :

Variable name	Derivation

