--	---

STAR – Statistical Analysis Plan
V3, June 2023

Page 74 of 96

	
treatment prescribed as part of the protocol at Vadd1 = Yes
 
AND
 
 ○ Reason: Treatment of a flare-up of the disease documented by a rheumatologist in Vadd1 = Yes ○ OR Treatment of a flare-up by the attending physician at Vadd1 = Yes 
OR
 
 ● Was treatment with corticosteroids (other than hydrocortisone) IV or IM received in addition to the treatment prescribed as part of the protocol at Vadd2 = Yes 
AND
 
 ○ Reason: Treatment of a flare-up of the disease documented by a rheumatologist in Vadd2 = Yes ○ OR Treatment of a flare-up by the attending physician at Vadd2 = Yes 
It will take the value “No” in all other cases.

Patient having received at least one corticosteroid infiltration during the protocol (yes/no)
	
From the variables: Total number of infiltrations received in relation to RA over the duration of post-randomization follow-up [Derived Variable], we define two modalities:
 
" If yes :
 
 ● Total number of infiltrations received in relation to RA over the duration of post-randomization follow-up > 1 
" Not if :
 
 ● Total number of infiltrations received in relation to RA over the duration of post-randomization follow-up = 0

Need for GC salvage treatment during protocol (yes/no)
	
From the following derived variables: Taking at least one long-term oral corticosteroid during the protocol (yes/no) [Derived Variable], Taking at least one attack corresponding to rescue treatment during the protocol (yes /no) [Derived Variable], Taking at least one short GC therapy not corresponding to rescue treatment for the entire duration of the study (yes/no) [Derived Variable], Taking at least one treatment by IV or IM corticosteroid during the protocol (yes/no) [Derived Variable], Patient having received at least one corticosteroid infiltration during the protocol (yes/no) [Derived Variable], we define two modalities:
 
" If yes :
 
 ● Taking at least one long-term oral corticosteroid during the protocol = Yes ● OR Taking at least one attack corresponding to rescue treatment during the protocol = Yes

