STAR – Statistical Analysis Plan
V3, June 2023

Page 75 of 96

	
 • OR Taking at least one short GC therapy not corresponding to rescue treatment for the entire duration of the study = Yes • OR Taking at least one IV or IM corticosteroid treatment during the protocol = Yes • OR Patient having received at least one corticosteroid infiltration during the protocol = Yes 
" Not if :
 
 • Taking at least one long-term oral corticosteroid during the protocol = No or missing • AND Taking at least one attack corresponding to rescue treatment during the protocol = No or missing • AND Taking at least one short GC therapy not corresponding to rescue treatment for the entire duration of the study = No or missing • AND Taking at least one IV or IM corticosteroid treatment during the protocol = No or missing • AND Patient having received at least one corticosteroid infiltration during the protocol = No or missing
--	---

The proportion of patients supplemented with prednisone will be compared in the two groups using a Chi2 test after verification of the application conditions: theoretical numbers greater than 5. In the event that the application conditions are not respected, an exact test of Fisher will be used.

The significance threshold for the tests is set at 0.05.

STAR – Statistical Analysis Plan
V3, June 2023

Page 76 of 96

5) Proportion of patients who received intra-articular injections

Proportion of patients who required intra-articular or periarticular GC injection during RA-related protocol.

Variable name	Derivations
Intra-articular injections (yes/no)	
From the variables “ Total number of infiltrations received in relation to RA over the duration of post-randomization follow-up ” [Derived variable], we define two modalities:
 
" If yes :
 
 • “ Total number of infiltrations received in relation to RA over the duration of post-randomization follow-up ” ≥ 1 
" Not if :
 
 • “ Total number of infiltrations received in relation to RA over the duration of post-randomization follow-up ” = 0

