The proportion of patients having received intra-articular injections will be compared in the two groups using a Chi2 test after verification of the application conditions: theoretical numbers greater than 5. In the event that the application conditions are not respected , a Fisher exact test will be used.

The significance threshold for the tests is set at 0.05.

Off-protocol analysis:

For exploratory purposes, without implementing a statistical test, we will carry out a descriptive analysis of secondary judgment criteria no. 4 and no. 5 in a combined manner.

Variable name	Derivations
Intra-articular injections and Need for short GC salvage treatment (yes/no)	
From the variables “ Need for a short rescue treatment with GC during the protocol ” [Derived variable] and “ Intra-articular injections ” [Derived variable], we define two modalities:
 
" If yes :
 
 • “ Need for short GC salvage treatment during protocol ” = Yes OR • “ Intra-articular injections ” = Yes 
" Not if :
 
 • “ Need for short GC salvage treatment during protocol ” = No AND • “ Intra-articular injections ” = No

The results will be presented using numbers and percentages.

STAR – Statistical Analysis Plan
V3, June 2023

Page 77 of 96

6) Proportion of patients who had at least one relapse during the protocol

Proportion of patients with a flare-up confirmed by the clinician. In the event of flare-up symptoms, the patient will have an additional visit to their center. For DAS28 >3.2, a surge will be confirmed. A flare will also be diagnosed if the DAS28 is >3.2 at any scheduled visit.

Variable name	Derivations

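### Secondary endpoint 4 (extra prednisone for flares) is also met by RA joint injections alone, so its derivation departs from its objective and overlaps endpoint 5

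*SAP*

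**What the plan says.** SAP, Secondary Objectives, no. 4: "To compare proportion of patients needing extra prednisone to control flares".

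SAP, Endpoints, secondary endpoints 4 and 5, lists two separate items: "Proportion of patients who needed a short rescue GC treatment during the protocol" and "Proportion of patients who needed a GC intra-articular or peri-articular injection during the protocol related to the RA".

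SAP, analyses of secondary criteria, section 4, opens with a wider description, "Proportion of patients who required salvage GC treatment during the protocol". It then derives one composite variable, *Need for GC salvage treatment*, from five components joined by OR: long-term oral corticosteroid, rescue course, short course outside the rescue scheme, IV or IM corticosteroid, and joint infiltration. The last enters as "Patient having received at least one corticosteroid infiltration during the protocol = Yes". That component is itself Yes when "Total number of infiltrations received in relation to RA over the duration of post-randomization follow-up > 1" and No when the same count is 0. The No rule of the composite accepts each component as either No or missing. The result is announced as follows: "The proportion of patients supplemented with prednisone will be compared in the two groups", at the 0.05 level.

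Section 5 uses the same count for endpoint 5, with one or more as Yes. It then adds an untested exploratory analysis: "we will carry out a descriptive analysis of secondary judgment criteria no. 4 and no. 5 in a combined manner". That variable is Yes if either endpoint is Yes.

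**The concern.** A joint injection is neither extra prednisone (the objective) nor a short rescue course (the endpoint list), and the plan already has an endpoint for it. Once injections count towards endpoint 4, the tested proportion answers a different question from the one stated, under a label that is untrue for patients who had injections only. Endpoints 4 and 5 then share a source variable. If one arm had more injections and the same systemic GC use, endpoint 4 could show a difference that a reader would take as a difference in prednisone need.

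The indication also differs. The four other components each require that the GC was given for a flare or, for the oral ones, taken by the patient for RA pain. The infiltration count, derived in the primary endpoint section, requires only that the injection was related to RA.

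**Working it through.** No figure in the plan bears on this point, so the check is of the derivation logic, followed by an illustration of size.

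**Step 1. Truth table.** *Other GC* means Yes on any of the four non-injection components. *EP4* and *EP5* are endpoints 4 and 5. A count that meets neither the Yes nor the No rule is taken as missing.

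| Other GC | RA injections | EP4 as coded (> 1) | EP4 if ≥ 1 | EP4 without injections | EP5 | 4 or 5 |
|---|---|---|---|---|---|---|
| No | 0 | No | No | No | No | No |
| No | 1 | No | Yes | No | Yes | Yes |
| No | 2 or 3 | Yes | Yes | No | Yes | Yes |
| Yes | 0 | Yes | Yes | Yes | No | Yes |
| Yes | 1, 2 or 3 | Yes | Yes | Yes | Yes | Yes |

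- As coded, two or more injections with no other GC give endpoint 4 = Yes.
- As coded, exactly one injection with no other GC leaves the component unclassified. It passes the No-or-missing rule, so endpoint 4 is No while endpoint 5 is Yes. This is the only cell of the eight in which the combination differs from endpoint 4.
- With ≥ 1, as the component's name says, every endpoint 5 Yes is also an endpoint 4 Yes, and the combination equals endpoint 4 in all eight cells.
- With injections removed, the combination adds to endpoint 4 every patient with at least one injection and no other GC.

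**Step 2. Size.** The documents give no rates for injections or for other GC, so the following rests on assumed values.

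- Simple count: the SAP plans 51 patients per arm. Five injection-only patients who meet the rule move from No to Yes: 5 / 51 = 9.8 percentage points.
- Range: let r be the proportion with other GC and q the proportion who meet the injection component, taken as independent. Endpoint 4 with injections = 1 − (1 − r)(1 − q), against r without them.
  - r = 0.20, q = 0.10: 1 − 0.80 × 0.90 = 0.28.
  - r = 0.40, q = 0.30: 1 − 0.60 × 0.70 = 0.58.
  - So with r from 20% to 40% and q from 10% to 30%, endpoint 4 reads 28% to 58% instead of 20% to 40%.
- Arm difference from injections alone: with r = 0.30 in both arms and q = 0.10 against 0.30, endpoint 4 is 1 − 0.70 × 0.90 = 0.37 against 1 − 0.70 × 0.70 = 0.51. That is a 14-point difference with no difference in other GC.

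Under the coding as written, q is the proportion with two or more injections. It cannot exceed the proportion with one or more, so the shift is no larger and usually smaller.

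**The case against.** The strongest defence is that the composite was widened on purpose. The analysis section drops the word *short*, speaks of salvage GC in general, and says that several compliance variables will be combined. On that reading, injections are one more form of salvage GC and only the label is loose. This stands as far as it goes, and it makes relabelling a legitimate repair. It does not remove the conflict with the objective, the endpoint list and the wording of the test. The primary endpoint also keeps injections (Modality 2) and short GC courses (Modality 3) apart.

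A reader might go further and infer that endpoint 4 duplicates endpoint 5, or that the 4-or-5 combination is empty. The documents do not support either. Endpoint 4 has four other components, so the two endpoints overlap and are not the same variable. As coded, neither contains the other, and the combination still adds patients with exactly one injection and no other GC. The combination also names a *short* salvage variable that is not derived under that name. If a variable restricted to short courses was meant, it is undefined and the identity with endpoint 4 need not hold.

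The consequences are also bounded. Endpoint 5 is tested and reported on its own, so a difference in injections would remain visible. The combination is exploratory and untested.

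**Conclusion.** The point holds as a mismatch between objective, label and derivation in one tested secondary endpoint. RA-related injections alone, two or more as coded, make a patient count as supplemented with prednisone, without the flare or RA-pain reason that the other components require. Endpoint 4 therefore overlaps endpoint 5, and a difference in injections can appear as a difference in prednisone need.

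The conflict between the component's name (at least one) and its coding (more than one) is a separate error that has to be settled at the same time. The statement that the combination equals endpoint 4 holds only after that correction, and only if the *short* salvage variable is the one derived in section 4.

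The sizes shown are illustrations on assumed rates and an assumed independence. The primary endpoint has its own derivation and is not affected. The change is worth making but does not threaten the main conclusion of the trial.

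**What to change.** Preferred change:

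1. Delete the infiltration line from the Yes rule and from the No rule of *Need for GC salvage treatment*.
2. Report RA-related injections only under endpoint 5, with one or more as Yes.
3. Use the injection-free variable, by its exact derived name, in the 4-or-5 combination, which then carries information.
4. Label the tested result as additional systemic GC for flares. Deleting the injection line does not by itself restore a prednisone-only or short-course endpoint, because the long-term oral and the IV or IM components remain.

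Alternative, if injections are kept on purpose: relabel endpoint 4 as any additional GC including injections, correct > 1 to ≥ 1 in the infiltration component, and drop the 4-or-5 combination.

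Either way the cost is a few lines of derivation and labelling, plus the signed amendment that the SAP requires for a change. No new data are needed, and the work can be done blind to group.

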For the analysis of the FLARE doctor questionnaire:

In the ITT population, we will carry out a mixed linear model for repeated data modeling the results of the FLARE questionnaires as a function of the time of administration of the questionnaire (M1 to M12) and the randomization group. We will describe the evolution of the results according to the time of administration of the questionnaire by a graphical representation of these models, in which the time of administration (visit) will be considered as a categorical variable and in which we will take into account a potential interaction between the time of administration and the randomization group.

If the evolution of scores over time is linear and there is no interaction between the time of administration and the randomization group, we will carry out models with the time of administration as a continuous variable (in month). In this case, we will describe the result by estimating a coefficient β with a 95% confidence interval, corresponding to the average difference in scores between the groups between M1 and M12.

If these two conditions are not met (absence of interaction and non-linearity of the relationship), the results of the FLARE questionnaires will be described for each arm at M4 and M7. The difference in distribution between the two arms will be tested using a two-sided Student's test (or a Wilcoxon test if the conditions for applying the Student's test are not verified) for each of these 2 visits. The significance threshold for the tests is set at 0.05.

In the event of missing data on one of the items, the value of the missing item will be replaced by the median value of the item at the visit concerned according to the patient's randomization group.

One approach will be to add up the scores at each time. We will therefore obtain a cumulative sum of the scores. The difference in distribution of the cumulative sums between the two arms will be tested using a two-sided Student's test (or a Wilcoxon test if the conditions for applying the Student's test are not verified) for each of these 2 visits. The significance threshold for the tests is set at 0.05.

In the event of missing data we will use the following imputation methods:

- In the event of missing data on one of the items, the value of the missing item will be replaced by the median value of the item at the visit concerned according to the patient's randomization group.

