- In the event of missing data at one or more visits, we will impute the non-missing values of the randomization group from which the patient came at the visit in question by the median value.

Patient FLARE scores should have a large number of missing data (questionnaires poorly completed during follow-up). These scores present will be described in each group using the mean, standard deviation, median and interquartile range. In the event of missing data on one of the items, the value of the missing item will be replaced by the median value of the item at the visit concerned according to the patient's randomization group.

No bivariate analysis will be performed on these scores.

STAR – Statistical Analysis Plan
V3, June 2023

Page 79 of 96

8) Proportion of patients in remission or at low activity level according to the DAS28 at 7 and 12 months

Proportion of patients in remission and with low disease activity at 7 months and one year. Patients with a DAS28 < 2.6 will be considered in remission, patients with a DAS28 between 2.6 and 3.2 will be considered in LDA.

The DAS28 formula is as follows:

$$\text{DAS28} = (0.56 * \text{sqr}(\text{TJC})) + (0.28 * \text{sqr}(\text{SJC})) + (0.7 * \text{ln}(\text{VS})) + (0.014 * \text{GH})$$

Where **TJC** = Number of painful joints [CRFp72, p114]
SJC = Number of swollen joints [CRFp72, p114]
VS = the sedimentation rate [CRFp84, p126]
GH = overall health represents the patient's assessment of disease activity on a scale of 0 to 100 where 100 corresponds to maximum activity [CRFp81, p123].
 The DAS28 is calculated automatically in the e-CRF.

Variable name	Derivations
Remission according to DAS28 (Yes No)	
From the DAS28 scores at M7 and M12 (variable present in the database or programmed), we define two modalities:
 
 • " If yes : 
 ○ DAS28 < 2.6 • " Not if : 
 ○ DAS28 ≥ 2.6 
For each of times M7 and M12, a variable will be created using the same methods.

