Low level of activity according to DAS28 (yes/no)	
From the DAS28 scores at M7 and M12 (variable present in the database or programmed), we define two modalities:
 
 • " If yes : 
 ○ DAS28 ≥ 2.6 and < 3.2 • " Not if : 
 ○ DAS28 ≥ 3.2 ○ OR if DAS28 > 2.6 
For each of times M7 and M12, a variable will be created using the same methods.

Remission or low level of activity according to DAS28 (Yes No)	
From the variables " Remission according to DAS28 " and " Low activity level according to DAS28 " [Derived variable], we define two modalities:
 
" If yes :
 
 • " Remission according to DAS28 " = Yes OR • " Low activity level according to DAS28 " = Yes 
" Not if :
 
 • " Remission according to DAS28 " = No AND • " Low level of activity according to DAS28 " = No 
For each of times M7 and M12, a variable will be created using the same methods.

STAR – Statistical Analysis Plan
V3, June 2023

Page 80 of 96

The proportion of patients in remission or at a low level of activity will be compared in the two groups using a Chi² test after verification of the application conditions: theoretical numbers greater than 5. In the event that the application conditions are not not respected, a Fisher exact test will be used.

The significance threshold for the tests is set at 0.05.

STAR – Statistical Analysis Plan
V3, June 2023

Page 81 of 96

9) HAQ-DI score at 4, 7 and 12 months

Functional impairment assessed by the Health Assessment Questionnaire (HAQ) at baseline, 4, 7 months and one year.

The HAQ will be calculated at baseline [CRFp25-26], at 4 [CRFp49-50], 7 months [CRFp74-76] and one year [CRFp116-117], and is expressed as continuous data.

The HAQ-DI SCORE at inclusion 4, 7 and 12 months will be compared in the two groups using a Student t test if the application conditions are met and a non-parametric Mann-Whitney Wilcoxon test otherwise.

The significance threshold for the tests is set at 0.05.

STAR – Statistical Analysis Plan
V3, June 2023

Page 82 of 96

10) RAID score at 4, 7 and 12 months

Patient-reported outcomes assessed by the Rheumatoid Arthritis Impact of Disease (RAID) questionnaire at baseline, 4, 7 months, and 1 year.

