The RAID questionnaire will be calculated at baseline [CRFp27], 4 [CRFp51], 7 [CRFp76] and 12 [CRFp118] months and is expressed as continuous data.

The RAID SCORE at inclusion, 4, 7 and 12 months will be compared in the two groups using a Student t test if the application conditions are met and a non-parametric Mann-Whitney Wilcoxon test otherwise.

The significance threshold for the tests is set at 0.05.

STAR – Statistical Analysis Plan
V3, June 2023

Page 83 of 96

11) EQ-5D score at 4, 7 and 12 months

The EuroQol 5-Dimension Descriptive System (EQ-5D) will be completed at baseline [*CRFp31*], at 4 [*CRFp55*], 7 [*CRFp80*] and 12 [*CRFp27*] months. The EQ-5D questionnaire will be calculated at baseline, after 4, 7 and 12 months and is expressed as continuous data.

The EQ-5D scores at inclusion 4, 7 and 12 months will be compared in the two groups using a Student t test if the application conditions are met and a non-parametric Mann-Whitney Wilcoxon test otherwise.

The significance threshold for the tests is set at 0.05.

STAR – Statistical Analysis Plan

V3, June 2023

Page 84 of 96

12) FACIT-F score at 4, 7 and 12 months

Functional Assessment of Chronic Disease Therapy - Fatigue Scale (FACIT-F): The FACIT-F questionnaire explores patient-reported fatigue. It will be completed at baseline [CRFp28-30], at 4 [CRFp52-54], 7 [CRFp77-79] and 12 [CRFp119-121] months. It will be expressed as continuous data.

The responses to the FACIT-F questionnaire at inclusion 4, 7 and 12 months will be compared in the two groups using a Student t test if the application conditions are met and a non-parametric Mann-Whitney Wilcoxon test in the case. opposite.

The significance threshold for the tests is set at 0.05.

STAR – Statistical Analysis Plan
V3, June 2023

Page 85 of 96

13) Proportion of serious adverse events at 1 year

The next secondary outcome is the proportion of patients who experienced at least one serious adverse event over a 1-year period.

Variable name	Derivations
Serious adverse events (yes/no)	
From the tables “ Adverse events 1/3, 2/3, 3/3 ” [CRFp169-171] and the variable “ Severity (serious/non-serious) ” present in these same tables, we define 2 modalities:
 
" If yes :
 
 • Event title is not missing • AND if “G ravité ” = serious 
" Not if :
 
 • Event title is not missing • AND if “G delighted ” = not serious • OR if the event title is missing

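### FLARE cumulative sums are tested after missing visits are filled with the patient's own arm median, the FLARE fallback stops at M7, and HAQ, RAID, EQ-5D and FACIT-F are compared without their baseline scores

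*SAP*

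**What the plan says.** Secondary objective 7 in the SAP is "To compare the area under the curve of the means of the FLARE at one year with a self-assessment questionnaire". Item 7 of the secondary analyses then sets out, for the doctor FLARE questionnaire:

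- A linear mixed model over M1 to M12, first with visit as a category and a group-by-visit interaction. If the course is linear and there is no interaction, time becomes continuous and one coefficient with a 95% CI gives the average group difference.
- A fallback if those conditions are not met: "the results of the FLARE questionnaires will be described for each arm at M4 and M7", with a Student or Wilcoxon test at each of these two visits.
- A further analysis: "One approach will be to add up the scores at each time". "The difference in distribution of the cumulative sums between the two arms will be tested using a two-sided" Student test, or a Wilcoxon test; "The significance threshold for the tests is set at 0.05".
- Two fill rules after the cumulative-sum paragraph. A missing item takes the median of that item in the patient's own arm at that visit. For a missing visit, "we will impute the non-missing values of the randomization group from which the patient came at the visit in question by the median value". I read this as replacing the missing score by the median of the observed scores in the patient's arm.

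Patient-completed FLARE scores, where many missing data are expected, are only described.

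For the other scales, item 9 says "The HAQ-DI SCORE at inclusion 4, 7 and 12 months will be compared in the two groups using a Student t test" and item 10 says "The RAID SCORE at inclusion, 4, 7 and 12 months will be compared in the two groups using a Student t test", with Mann-Whitney as the alternative. Items 11 (EQ-5D) and 12 (FACIT-F) follow the same pattern. None of the four uses the baseline score in the later comparisons.

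**The concern.** There are three separate weaknesses.

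1. A fill with the arm's own median adds no information. It pulls the scores in each arm towards that arm's centre, and it copies the arm's sampling error into every filled value. A t or Wilcoxon test that takes the fills as data uses too small a standard error, so it rejects too often when the strategies do not differ.

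2. The fallback tests stop at M7. Randomization is at M1 and the hydrocortisone sequence lasts 3 + 3 months (SAP, sample size calculation), so M7 is about the end of that sequence. The later visits, M9 and M12, are the ones that bear on a one-year objective.

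3. Four scales have a pre-treatment score that is collected and then not used, except in a between-arm test at inclusion. In a randomized trial that test can only examine chance.

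At stake are the credibility of one FLARE p-value, the ability to answer objective 7 at one year, and the precision of endpoints 9 to 12.

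**Working it through.** **Inputs from the SAP.** 51 patients per arm; 20% anticipated loss to follow-up; alpha 0.05 per test; own-arm median fill; t or Wilcoxon test on the sums.

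**Assumptions, not in the SAP.** A missing-visit rate of 10, 20 or 30% (the 20% is borrowed from the loss to follow-up); five doctor FLARE visits at M1, M4, M7, M9 and M12, with M1 always observed; within-patient correlation 0.6, also 0.3 and 0.8; normal or log-normal scores.

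**Benchmark.** The SAP's only figure here is the nominal 0.05. In the null simulation, patients with all visits observed gave a t-test error of 0.042 to 0.053 with normal scores. The benchmark is therefore reproduced when nothing is filled.

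**Mechanism, one visit.** Let a fraction m be filled at the arm's centre.

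- True SE of the arm mean ≈ σ/√(n(1−m)).
- Naive SE ≈ σ√(1−m)/√n.
- Ratio of naive to true SE = 1−m.
- Type I error ≈ 2[1 − Φ(1.96(1−m))] = 0.078, 0.117 and 0.170 at m = 0.1, 0.2 and 0.3.

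This shows the direction only. The SAP does not clearly attach the visit fill to a single-visit test.

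**Five-visit sum, no true difference, correlation 0.6** (3,000 runs per cell, Monte Carlo SE about 0.005):

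| Missingness | 10% | 20% | 30% |
|---|---|---|---|
| Dropout reaching this rate by M12, t test | 0.063 | 0.079 | 0.100 |
| Intermittent, t test | 0.074 | 0.097 | 0.131 |
| Lost before M4, t test | 0.065 | 0.095 | 0.141 |
| Dropout, Wilcoxon | 0.070 | 0.093 | 0.121 |
| Intermittent, Wilcoxon | 0.073 | 0.109 | 0.142 |

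At 20% missing, the t test gives 0.078 to 0.107 with correlation 0.3 or 0.8, and 0.062 to 0.083 with skewed scores at correlation 0.6.

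**Which visits are summed.** The SAP says the sums are tested for each of two visits, which is unclear for a sum over all visits. If it means sums up to M4 and up to M7, 20% dropout gives only about 0.05 to 0.06. With 20% intermittent missing, a separate set of 8,000 runs gave 0.080 to M4, 0.093 to M7 and 0.102 to M12.

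**Fallback.** Randomization makes the expected difference between arms 0 at M1. If it is δ at a later visit, the group-by-time contrast is δ − 0 = δ. Any effect that emerges after M1 is therefore itself an interaction, and an interaction is what breaks the no-interaction condition. The fallback is likeliest to be used when there is an effect to describe, and it then tests M4 and M7 only. The trigger is also unclear: its parenthesis names non-linearity, although the condition in the preceding paragraph is linearity.

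**Endpoints 9 to 12.** Adjusting for baseline multiplies the variance of the group difference by 1 − r², where r is the baseline-to-follow-up correlation (assumed; the SAP gives none):

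- r = 0.3: 1 − 0.09 = 0.91, a 9% cut
- r = 0.5: 1 − 0.25 = 0.75, a 25% cut
- r = 0.7: 1 − 0.49 = 0.51, a 49% cut

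**The case against.** The strongest reply is that the first-listed FLARE analysis is already a repeated-measures model that needs no visit fill. This stands. A reader might infer that all FLARE p-values and intervals are too optimistic, but the SAP does not support that: the visit fill is written under the cumulative-sum approach, and the only planned FLARE interval belongs to the mixed model. Patient FLARE is not tested at all.

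A reader might also infer that the FLARE type I error simply doubles. That is too strong. The missing rate is assumed, dropout at 20% gives 0.079 (about 1.6 times nominal), and sums over early visits alone give less.

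It is tempting to say that the area under the curve is never estimated and that a plain sum misweights the visits. The first is overstated, because the continuous-time coefficient is a time-averaged difference. The second is minor: equal-weight and trapezoid sums correlate at 0.988, 0.996 and 0.998 for within-patient correlations of 0.3, 0.6 and 0.8. Nor is M1 as an outcome an error in itself. It dilutes the effect only in the continuous-time model without interaction.

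It can be said that the cumulative sum covers M9 and M12 even if the fallback does not. That holds only if all visits are summed, and the one-year answer would then rest on the test affected by the median fill.

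Finally, unadjusted randomized comparisons are unbiased, objectives 9 to 12 speak of medians, and a test at inclusion does not bias later ones. All of this is right. The third point is about efficiency, not validity.

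**Conclusion.** The point holds in three limited parts, all on secondary endpoints.

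1. The own-arm median fill makes the FLARE cumulative-sum test anti-conservative. For a five-visit sum with 20% missing and correlation 0.6, both assumed, the t-test error is about 0.08 to 0.10 instead of 0.05. It is smaller with less missingness or if only early visits are summed. The finding concerns this test and not the mixed model.
2. The fallback tests at M4 and M7 cannot answer a one-year objective, and they are likeliest to be invoked when the arms diverge after M1. This follows from the text and needs no assumed rate.
3. Endpoints 9 to 12 give up precision that the collected baseline scores would supply: 9%, 25% or 49% of the variance at assumed r of 0.3, 0.5 or 0.7. The tests at inclusion add nothing.

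The change should be made before the analysis is run.

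**What to change.** **FLARE.** Delete the visit-level arm-median fill and the M4/M7-only fallback. Base inference on the planned mixed model, fitted to observed data, with visit as a category, group-by-visit interaction and M1 as baseline. Report the group difference at each visit through M12 and a time-averaged (area-under-the-curve) contrast, each with a 95% CI. The model still assumes that missingness depends only on observed data, and the SAP should say so. If a cumulative sum is kept as a description, state which visits it covers. Fill a missing item from the patient's own answered items, as the SAP already does for one missing RAID scale and, by prorating, for FACIT-F.

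**HAQ, RAID, EQ-5D, FACIT-F.** Compare the arms after adjustment for the baseline score, by ANCOVA or a repeated-measures model, with a rank-based ANCOVA if residuals are clearly non-normal. Replace the tests at inclusion by description.

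**Cost.** SAP wording and modest programming; no new data. For endpoints 9 to 12 the estimate becomes a difference in means where the objectives speak of medians, so those objectives need matching wording.
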